#### 3.7 Trial Procedures

This is a multicenter, open-label trial designed to assess the safety and tolerability of oral brexpiprazole (OPC-34712) (2-4 mg/day) as treatment in adults with bipolar I disorder. The trial will be conducted on an outpatient basis. The trial comprises a 26-week open-label treatment period with a 21 ( $\pm$  2) day follow-up.

Trial assessment time points are summarized in Table 3.7-1 (open-label treatment phase [Phase B]) and Table 3.7-2 (conversion phase [Phase A]).

34

Table 3.7-1	Schedule	of Assessm	ents - O	pen-label	Treatmen	nt (Phase	B)			
Assessment	Screening	Phase B	Open-Label Treatment Phase Trial Week Visit (± 2 days)				/s)	Follow-up		
	Baseline a (Rollover)	Baseline a (De Novo)	1	2	4	8	12	18	26 / ET b	21 (± 2) days c
ENTRANCE CRITER				_	,					
Informed consent	$\mathbf{X}^{\mathbf{d}}$									
Inclusion/exclusion criteria	X	X								
Medical history	Xe									
CCI		 			I.		1	1	- I	
			_		-					
SAFETY				 	· L			1		I
Physical examination	X f	X g							X	
Waist circumference	X f	X g							X	
Vital signs i	X f	X g	X	X	X	X	X	X	X	
12-lead ECG j	X f	X g					X		X	
Clinical laboratory tests k	X f,l	X g,l					X m		X m	
HbA1c	X f,l	$X^{g,l}$					X m		X m	
Drug screen/blood alcohol n	X f	X g			X		X		X	
Urine pregnancy test (WOCBP only) 	X f	X g	X	X	X	X	X	X	X	
CCI										

Confidential - Proprietary Information

35

Table 3.7-1				P		ıt (Phase ]				
Assessment	Screening	Phase B	Open-Label Treatment Phase Trial Week Visit (± 2 days)						Follow-up	
	/	Baseline a								21 (± 2) days
	Baseline a	(De								
	(Rollover)	Novo)	1	2	4	8	12	18	26/ ET b	
CCI										
Adverse events q	X	X	X	X	X	X	X	X	X	X
Concomitant medications	X	X	X	X	X	X	X	X	X	X
OTHER		•		•			•	•		•
CCI										
										
					•					
Dose adjustment r			X	X	X	X	X	X	X	
Register visit in IWRS	X	X	X	X	X	X	X	X	X	
IMP dispensing	X	X	X	X	X	X	X	X		
IMP accountability			X	X	X	X	X	X	X	

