<sup>aFor rollover subjects, screening for Trial 331-201-00083 occurs simultaneously with baseline which will be at the same day as the Day 21 (Week 3) visit of Trial 331-201-00080 or Trial 331-201-00081. Separate screening and baseline visits are required for de novo subjects to allow for completion of eligibility assessments and washout of prohibited concomitant medications, if applicable. The enrollment of de novo subjects at any site will not be permitted until initiation and notification by the sponsor.

Confidential - Proprietary Information

36

<sup>bIf a subject discontinues early before Week 26, procedures noted for Week 26 must be completed at the ET visit. Attempts should be made to complete ALL evaluations, particularly efficacy assessments, for the Week 26/ET visit prior to the administration of any new psychotropic medications. However, if the subject receives a new antipsychotic prior to ET procedures, no efficacy assessments should be done. Any prohibited medications started before the end of the trial assessments should be documented as a protocol deviation in the source notes.

<sup>gBaseline assessment will be performed at baseline of Phase B for de novo subjects who enter Phase B directly after screening, but will be obtained from the Conversion Week 4 visit of Phase A for subjects who participate in Phase A.

Vital signs include body weight, body temperature, systolic blood pressure (SBP), diastolic blood pressure (DBP), and heart rate. Blood pressure and heart rate will be measured in the following order: supine and standing after the subject has been in each position for at least 3 minutes. Vital signs scheduled for the same visit as blood samples are to be completed before blood is drawn.

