## 3.7.1.3 Post-treatment Follow-up Period

Subjects will be contacted to monitor for safety events via telephone contact or clinic visit (investigator's discretion) for 21 ( $\pm$  2) days after the last dose of IMP. Adverse

Confidential - Proprietary Information

52

events and concomitant medications will be recorded. This contact also applies to subjects withdrawn prematurely from the trial.

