#### 3.7.4 Prior and Concomitant Medications

The investigator will record all medications and therapies taken by the subject from 30 days prior to the first dose of IMP through the end of the evaluation period (defined as the time period during which subjects are evaluated for primary and/or secondary objectives) on the case report form. The investigator will record all medications and therapies taken by the subject for treatment of an AE or which caused an AE until the end of the trial (defined as the last date of contact or date of final contact attempt) on the case report form.

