# 5.7 Follow-up of Adverse Events

For this trial, information on AEs will be followed for up to 21 days after the last dose of IMP has been administered.

Confidential - Proprietary Information

73

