## 7.4 Primary and Secondary Endpoint Analyses

# 7.4.1 Primary Endpoint Analysis

The primary safety endpoint analysis is the frequency and severity of AEs in the open-label treatment phase (Phase B). All AEs will be coded using the Medical Dictionary for Regulatory Activities (MedDRA) preferred term. The incidence of TEAEs will include the following summaries:

- TEAEs by severity
- Potentially drug-related TEAEs
- TEAEs with an outcome of death
- Serious TEAEs
- Discontinuations due to TEAEs

A TEAE is defined as an AE that starts after the first dose of IMP or an AE that is reported at baseline and increases in intensity or becomes serious or trial drug-related or results in death, discontinuation, interruption, or reduction of IMP.

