9.1 Adverse Events

All adverse events will be coded by System Organ Class (SOC) and Preferred Term (PT) according to the Medical Dictionary for Regulatory Activities (MedDRA). AEs that are sexspecific, e.g., ovarian cancer, will have their incidence rates evaluated for the specific sex.

Treatment-emergent AEs (TEAEs) are defined as AEs with an onset date on or after the first dose of IMP. In more detail, TEAEs are all adverse events which started after start of IMP; or if the event was continuous from baseline and was worsening, serious, study drug related, or resulted in death, discontinuation, interruption or reduction of study therapy. Adverse events occurring up to 21 days after the last day of IMP will be included in the summary tables.

The incidence of the following events in the open-label treatment phase will be summarized using the Safety Sample:

- a) TEAEs
- b) TEAEs by severity
- c) TEAEs potentially causally related to the IMP
- d) TEAEs with an outcome of death
- e) Serious TEAEs
- f) TEAEs leading to discontinuations of the IMP

The above summaries (b), (e) and (f) will also be prepared for TEAEs potentially causally related to the IMP.

In addition, incidence of TEAE during the open-label treatment phase of at least 5% by SOC and PT will be provided.

Incidence of TEAEs by SOC and PT will be summarized for sex, race, age and region subgroups.

EPS-related AEs will be grouped into five categories.

- 1) Dystonic Events, which include cervical spasm, dystonia, emprosthotonos, muscle contractions involuntary, muscle rigidity, muscle spasms, muscle spasticity, myotonia, nuchal rigidity, oculogyration, opisthotonos, pleurothotonus, risus sardonicus, torticollis, and trismus;
- 2) Parkinsonian Events, which include akinesia, asterixis, athetosis, bradykinesia, cogwheel rigidity, essential tremor, extrapyramidal disorder, freezing phenomenon, gait festinating, hyportonia, hypokinesia, hypokinesia neonatal, intention tremor, masked facies, parkinson's

Confidential - Proprietary Information

disease, parkinsonian crisis, parkinsonian gait, parkinsonian rest tremor, parkinsonism, tremor, and tremor neonatal;

- 3) Akathisia Events, which include akathisia, hyperkinesia, and psychomotor hyperactivity;
- 4) Dyskinetic Events, which include ballismus, buccoglossal syndrome, choreoathetosis, clumsiness, dyskinesia, dyskinesia neonatal, dyskinesia oesophageal, fumbling, nodding of head, on and off phenomenon, and tardive dyskinesia;

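### SAP 9.1 puts adverse events from the 21 days after the last dose into tables labelled open-label treatment phase, with no visible split from on-treatment events

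*SAP*

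**What the plan says.** **AE window.** SAP 9.1 states: "Adverse events occurring up to 21 days after the last day of IMP will be included in the summary tables". It introduces the list of summaries (a) to (f) with: "The incidence of the following events in the open-label treatment phase will be summarized using the Safety Sample". The same section defines five EPS groupings. No readable text divides events by onset before or after the last dose. The contents of SAP section 10 (Conventions) and section 12 (list of tables) are not visible.

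**Primary analysis.** Protocol 7.4.1 gives it as the "frequency and severity of AEs in the open-label treatment phase (Phase B"). Protocol 3.7 says "The trial comprises a 26-week open-label treatment period" and names the 21 (± 2) day follow-up alongside it. Table 3.7-1 gives follow-up its own column.

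**AE collection.** Protocol 5.7: "information on AEs will be followed for up to 21 days after the last dose of IMP has been administered".

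**Other antipsychotics.** Protocol 3.2.2.1 requires withdrawal of a subject who needs additional antipsychotic treatment, and 3.7.1.3 applies the follow-up contact to subjects withdrawn early. Table 3.7-1, footnote b, foresees the switch: "if the subject receives a new antipsychotic prior to ET procedures, no efficacy assessments should be done".

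**Medication recording.** Protocol 3.7.4 records all medications "through the end of the evaluation period (defined as the time period during which subjects are evaluated for primary and/or secondary objectives"), and after that only those that treated or caused an AE. Protocol 3.7.1.3 says of the follow-up contact that "events and concomitant medications will be recorded", and Table 3.7-1 marks concomitant medications in the follow-up column. SAP 9.6 plans a tabulation of medications taken after study therapy.

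**The concern.** The trial is uncontrolled, its primary endpoint is AEs, and it has no secondary endpoints. The period over which events count is therefore one of its main analytic choices. As written, the SAP tables carry the label of the treatment phase but cover that phase plus three weeks off drug. A reader could not recover from them the Phase B result that Protocol 7.4.1 names.

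The content of those three weeks matters in this population. A subject withdrawn because another antipsychotic was needed may be taking it during the window. An akathisia or parkinsonian event starting then would appear in the open-label tables and the EPS groupings as an event on brexpiprazole. Footnote b bars efficacy ratings once a new antipsychotic has been given. No comparable rule is visible for AEs, or for the last-visit safety summaries planned in SAP section 9.

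Telling such events apart needs the start date of the replacement drug. That is where the conflict between Protocol 3.7.4 and the follow-up schedule matters.

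**Working it through.** The documents state no figure for this point, so there is none to reproduce. The check sets the passages side by side and then gives a sense of scale.

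**1. Do the two periods differ?** Yes. Protocol 7.4.1 names Phase B, which Protocol 3.1 and 3.7 set at 26 weeks (182 days), with follow-up named apart. SAP 9.1 adds 21 days. SAP 9.6 itself distinguishes medications during the open-label treatment phase from those after study therapy, so the same phase is bounded one way for medications and another way for AEs.

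**2. Can the window contain time on another antipsychotic?** Yes. Withdrawal is mandatory when one is needed (3.2.2.1), follow-up continues (3.7.1.3), and footnote b expects that a new drug may even precede the early-termination visit. The documents do not say how many subjects this affects.

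**3. Is the replacement drug recorded?** The passages disagree. Protocol 3.10 defines the treatment period in nearly the same words that 3.7.4 uses for the evaluation period, and ties completion to the Week 26 visit. Read that way, 3.7.4 leaves out a replacement antipsychotic that neither treated nor caused an AE. Protocol 3.7.1.3 and Table 3.7-1 would record it.

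**4. Scale.** Inputs from Protocol 3.3.1: about 384 enrolled and 175 completing.
- Implied non-completion: 384 − 175 = 209, and 209/384 = 54.4%.
- Share of one subject's counted time falling after the last dose = 21/(treated days + 21):
  - completer: 21/203 = 10.3%
  - stopping at Week 12: 21/105 = 20.0%
  - stopping at Week 8: 21/77 = 27.3%
  - stopping at Week 4: 21/49 = 42.9%
- Share over all subjects = 384 × 21 / (175 × 182 + 209 × m + 384 × 21) = 8064 / (31850 + 209m + 8064). Here m is the mean treated days of non-completers. The documents do not give it, so it is assumed:

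| Assumed m (days) | Treated days | Post-dose share |
|---|---|---|
| 28 | 37702 | 8064/45766 = 17.6% |
| 91 | 50869 | 8064/58933 = 13.7% |
| 154 | 64036 | 8064/72100 = 11.2% |

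A constant dropout hazard, also an assumption, falls inside this range. The weekly rate is −ln(175/384)/26 = 0.0302, mean exposure is (209/384)/0.0302 = 18.0 weeks, and the share is 3/(18.0 + 3) = 14.3%.

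All of these figures give every subject a full 21 days. They are shares of time under observation, not of events or of affected subjects.

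**The case against.** The strongest reply is that the window is legitimate. Protocol 5.7 follows AEs for 21 days after the last dose, 5.7.2 does the same for SAEs, and the TEAE definition in 7.4.1 has no end date, so the SAP only bounds an open definition. This stands: the window is not an error.

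A reader might infer more than the documents support on five further points.
- *That full medication recording stops.* Protocol 3.7.1.3, Table 3.7-1 and SAP 9.6 all provide for post-treatment medications, and even 3.7.4 keeps those that treated or caused an AE. Because AEs are the primary endpoint and are followed for 21 days, the evaluation period could also be read as reaching follow-up. The supportable statement is that the passages conflict.
- *That many early leavers are on another drug.* This is unquantified, and Protocol 3.8.3.2 and 3.8.3.3 list many other reasons for stopping.
- *That quiet off-drug time dilutes the results.* SAP 9.1 plans by-subject incidence, and no readable text plans person-time rates.
- *That ordinary illness recurrence inflates the tables.* Protocol 5.2 counts exacerbation as an AE only when its features are unusual, severe or unexpected.
- *That last-visit values come from the 21-day window.* The follow-up contact schedules no laboratory or weight measurement, and footnote b asks for all evaluations before any new psychotropic. The issue is confined to early-termination visits held after a switch.

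Summary (c), and the repeats of (b), (e) and (f) for IMP-related events, do give some separation. It rests on investigator causality rather than on dates, and it leaves (a), (d) and the unrestricted (b) and (e) as they are. Finally, a split may exist in SAP section 10 or 12, which cannot be read. Section 9.1 governs the primary endpoint and should still state it.

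**Conclusion.** The point holds in a limited form. In the readable text, SAP 9.1 places post-dose events in tables labelled as the open-label treatment phase without separating them, while Protocol 7.4.1 names Phase B as the primary period. Some of those events may arise on a replacement antipsychotic. Protocol 3.7.4 also conflicts with 3.7.1.3, Table 3.7-1 and SAP 9.6 on medication recording after treatment.

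The post-dose window is about 11% to 18% of AE observation time. This assumes the planned 175 completers of 384, non-completers averaging 28 to 154 treated days, and full follow-up for everyone. It does not measure bias in any planned table, and the documents allow no estimate of how many events are affected. No result is invalidated. The change is still worth making, because it delivers the period the protocol names and loses nothing.

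**What to change.** - **SAP 9.1:** present summaries (a) to (e) and the EPS groupings for onset through the last open-label dose date (the Phase B result) and for onset 1 to 21 days after it, and keep the combined total. Summary (f) needs no split, since an event starting after the last dose cannot normally have caused stopping. Flag events that start after another antipsychotic was begun.
- **SAP section 9:** flag last-visit safety values taken after a new antipsychotic.
- **Protocol 3.7.4:** reconcile it with 3.7.1.3 and Table 3.7-1 so that psychotropic medications are recorded through the follow-up contact. If any site has applied the narrower reading, footnote that the flag may be incomplete.

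The cost is one extra column and minor wording changes. The split uses onset and dose dates already planned for collection. The flags use medication dates that 3.7.1.3 and Table 3.7-1 already call for. The 21-day window and the combined figure remain.

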# 2 Trial Rationale and Objectives

#### 2.1 Trial Rationale

Current guidelines for the treatment of acute mania in bipolar I disorder advocate first-line use of atypical antipsychotics, such as aripiprazole, as monotherapy or in combination with lithium or divalproex. 2,3,4,5

Brexpiprazole (OPC-34712) is a novel atypical antipsychotic that is a serotonin-dopamine activity modulator and is indicated in the US as monotherapy for the treatment of schizophrenia in adult patients (2-4 mg/day) and as an adjunctive therapy to antidepressants for the treatment of MDD (2-3 mg/day). Like other atypical antipsychotics that have demonstrated efficacy across the indications of schizophrenia, MDD, and bipolar I disorder, brexpiprazole's (OPC-34712) specific receptor activity profile likely correlates with its established efficacy in schizophrenia and MDD, and may also prove to be an effective target for the treatment of the acute mania of bipolar I disorder. This 26-week, multicenter, open-label trial will be conducted to evaluate the long-term safety and tolerability of brexpiprazole (OPC-34712) for the treatment of subjects with bipolar I disorder.

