#### 3.3 Trial Population

# 3.3.1 Number of Subjects and Description of Population

It is estimated that approximately 384 rollover subjects may be enrolled into Trial 331-201-00083 to achieve a target completion of approximately 175 subjects at 6 months at approximately 90 trial sites in North America and the rest of world (ROW). Men and women 18 to 65 years of age with a Diagnostic and Statistical Manual of Mental Disorders, Fifth Edition (DSM-5) diagnosis of bipolar I disorder will be enrolled in the trial and will include rollover subjects from the double-blind, phase 3 efficacy trials (ie, Trials 331-201-00080 or 331-201-00081). In the event the sponsor determines that the enrollment rate of rollover subjects will not be sufficient to meet the target completion of approximately 175 subjects at 6 months, de novo subjects may be enrolled at select sites. The enrollment of de novo subjects at any site will not be permitted until initiation and notification by the sponsor.

Diagnosis will be confirmed by the Mini International Neuropsychiatric Interview (MINI) and a history of at least 1 previous manic episode with or without mixed features and manic symptoms of sufficient severity to require one of the following interventions: hospitalization or treatment with a mood stabilizer, or treatment with an

Confidential - Proprietary Information

26

<sup>bOption to titrate to 2 to 4 mg (ie, 2 mg, 3 mg, or 4 mg) based on clinical response and tolerability; changes must occur in 1 mg/day increments. Increases up to 4 mg/day may occur no earlier than Day 7.

antipsychotic agent. Eligible subjects must not currently have severity of bipolar symptoms that, in the opinion of the investigator, would require hospitalization. Approximately 60% of subjects will be enrolled from North America and 40% of subjects will be enrolled from the rest of world (ROW).

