## 3.10 Definition of Completed Subjects

The treatment period is defined as the time period during which subjects are evaluated for primary and/or secondary objectives of the trial irrespective of whether or not the subject actually consumed all doses of the IMP. Subjects who are evaluated at the last scheduled visit during the treatment period will be defined as trial completers. For purposes of this trial, subjects who complete the Week 26 visit will be defined as trial completers.

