5.1 Data Sets for Analysis

The following datasets are defined for this trial:

- Enrolled Sample, which comprises all subjects who sign an ICF for the trial.
- Safety Sample, which comprises all subjects who will receive at least 1 dose of IMP.

6 Study Conduct

There are no de novo subjects enrolled in the study.

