6.1 Subject Disposition, Completion Rate and Reasons for Discontinuation

Subject disposition will be summarized for the Enrolled Sample by parent study treatment group for rollover subjects and overall.

Confidential - Proprietary Information

8

Subject completion rate and reasons for discontinuation will be summarized for the Enrolled Sample by parent study treatment group for rollover subjects and overall.

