9.7 Extent of Exposure

[figure not shown]
The start date of the open-label study therapy - brexpiprazole - will be the first day of dosing during the open-label treatment phase. The number and percentage of patients who receive study medication during the open-label treatment phase, will be presented by week. Each dosing week will be based on the actual week; i.e., Day 1-7 in Week 1, Day 8-14 in Week 2, etc. This summary will be performed on the Safety Sample.

The mean daily dosage will be summarized by week using descriptive statistics. The mean daily dosage per patient per week will be determined for each week of the study. This will be calculated by dividing the sum of individual total doses by the number of days in the week interval. The summary will contain the number of patients receiving study medication during the open-label treatment phase, and the mean and range of the mean daily dose for each week.

Confidential - Proprietary Information

17

[figure not shown]

Confidential - Proprietary Information

10 July 2019

Until the information herein is released by Otsuka to the public domain, the contents of this document are Otsuka confidential information and should not be duplicated or re-distributed without prior written consent of Otsuka.

18

Confidential - Proprietary Information

19

10 July 2019

Until the information herein is released by Otsuka to the public domain, the contents of this document are Otsuka confidential information and should not be duplicated or re-distributed without prior written consent of Otsuka.

Confidential - Proprietary Information

20

11 Potential Clinical Relevance Criteria from Protocol

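### Adverse events are planned only as crude percentages of treated subjects, although the planning figures imply that about 54% will not reach Week 26

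*SAP*

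**What the plan says.** SAP 9.1 introduces the treatment-emergent adverse event (TEAE) tables with "The incidence of the following events in the open-label treatment phase will be summarized using the Safety Sample". The Safety Sample is everyone given at least one dose. The tables cover all TEAEs and those that are related, serious, fatal or lead to discontinuation. There is also a breakdown by severity, a table limited to events of at least 5%, and subgroup tables. The counting window runs past treatment: "Adverse events occurring up to 21 days after the last day of IMP will be included in the summary tables".

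For expected follow-up, Protocol 3.3.1 estimates that "approximately 384 rollover subjects may be enrolled into Trial 331-201-00083 to achieve a target completion of approximately 175 subjects at 6 months". Protocol 3.10 fixes the meaning of completion: "subjects who complete the Week 26 visit will be defined as trial completers". Protocol 2.1 says the 26-week trial is run to "evaluate the long-term safety and tolerability of brexpiprazole (OPC-34712) for the treatment of subjects with bipolar I disorder".

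Two other SAP sections bear on length of follow-up. SAP 9.7 states: "The number and percentage of patients who receive study medication during the open-label treatment phase, will be presented by week". SAP 6.1 states: "Subject completion rate and reasons for discontinuation will be summarized for the Enrolled Sample by parent study treatment group for rollover subjects and overall". Neither is connected to the adverse-event tables.

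**The concern.** The SAP speaks of incidence without defining it. The Safety Sample denominator and the 5% threshold point to one reading: subjects with an event divided by subjects dosed. The one mention of incidence rates in SAP 9.1 concerns sex-specific events and changes the denominator; it does not bring in person-time.

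Such a percentage mixes two things: how often the event occurs, and how long subjects stayed to be observed. If more than half leave before Week 26, a reader cannot tell a low event risk from short follow-up. Events that appear late suffer most, and they are much of what a 26-week trial adds to 3-week parent trials. SAP 9.1 itself lists tardive dyskinesia among its extrapyramidal terms.

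**Working it through.** **Implied non-completion.** Inputs are 384 and 175 (Protocol 3.3.1). 175/384 = 45.6% complete; 384 − 175 = 209, or 54.4%, do not. The visible text states no dropout rate, so this is inferred from the planning figures. It applies to enrolled subjects, and SAP 5.1 defines the "Enrolled Sample, which comprises all subjects who sign an ICF for the trial". Some may never be dosed; if only 350 are, non-completion is 1 − 175/350 = 50%.

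**Model (assumed, since the documents give neither event hazard nor dropout timing).** All 384 are dosed, the event hazard *h* is constant, dropout is exponential with hazard *d* and independent of the event, and events are counted to last dose plus 3 weeks for everyone.

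- *d* = −ln(0.4557)/26 = 0.0302 per week, giving a mean of 18.0 weeks on drug and 21.0 weeks to the end of the counting window.
- For a true 26-week risk *R*, *h* = −ln(1 − *R*)/26; for *R* = 10%, *h* = 0.00405 per week.
- Crude percentage = E[1 − exp(−*h*(min(*D*, 26) + 3))], where *D* is the dropout time in weeks. With exponential dropout this equals 1 − e^(−3*h*) × {[*d*/(*h*+*d*)] × (1 − e^(−26(*h*+*d*))) + e^(−26(*h*+*d*))}.
- For *R* = 10%: 1 − 0.9879 × {0.8818 × 0.5898 + 0.4102} = 8.1%.

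| True 26-week risk | Crude percentage | Shortfall, relative to true risk |
|---|---|---|
| 5% | 4.0% | 19% |
| 10% | 8.1% | 19% |
| 20% | 16.2% | 19% |
| 80% | 67.7% | 15% |

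**Varying the assumptions, true risk 10%.**

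| Scenario | Crude percentage |
|---|---|
| 30% leave uniformly over Weeks 0–4, the rest uniformly to Week 26 | 7.4% |
| All dropout uniform over Weeks 0–26 | 8.4% |
| All dropout uniform over Weeks 12–26 | 9.7% |
| Exponential dropout, 350 dosed | 8.4% |
| Exponential dropout, onset only in Weeks 0–4 | 10.0% |
| Exponential dropout, onset only from Week 12 | 7.2% |

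The last two rows are shortfalls of under 1% and of 28%.

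**The 5% table.** Setting the crude percentage to 5% and solving for *R* gives 6.2% with exponential dropout, and 6.8%, 5.9% and 5.2% with the early, uniform and late dropout shapes. Events with true risks below those values would drop out of this table on average, though they stay in the overall TEAE table.

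**Parent-group contrasts.** With assumed dropout of 50% in one group and 60% in another, the same true 10% shows as 8.38% and 7.73%, a difference of 0.65 points.

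**Do the proposed summaries recover the truth?** In 3,000 simulated trials of 384 subjects under the base model with a true risk of 10%, the crude percentage averaged 8.1% and the Week 26 Kaplan-Meier estimate 10.0% (SD 1.9 points). The rate averaged 21.2 per 100 patient-years, against a true value of 21.1.

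**Where Kaplan-Meier would mislead.** For TEAEs leading to discontinuation, other reasons for leaving are competing events. If 20% of dropout is due to adverse events (assumed), the actual proportion is 0.2 × 54.4% = 10.9%. Kaplan-Meier would give 1 − 0.4557^0.2 = 14.5%.

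**The case against.** The strongest reply is that no stated target is missed. The protocol's primary endpoint is the frequency and severity of adverse events, and the SAP reports exactly that. No 26-week risk is named as an estimand, and the reference to long-term safety is rationale text. This stands: the percentages are correct as descriptions and should stay.

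The 54% is also only a planning figure from the 2017 protocol. The July 2019 SAP does not repeat 384 in its visible text, and actual retention is unknown. This also stands; if retention proved better, the added columns would simply move closer to the crude ones.

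SAP 5.2 and the Section 12 table list are not shown, so an exposure-adjusted table may exist there. The point can cover visible text only.

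The size rests on independence between event and dropout, yet Protocol 3.8.3.2 names adverse events as a reason for stopping, and a subject who leaves because of an event has already been counted. If half of first events trigger dropout (assumed), simulation cuts the shortfall from 17% to 8% at a true risk of 60% and from 15% to 4% at 80%. At 10% it barely moves, from 19% to 18%. The 19% is therefore least reliable for the any-TEAE summary and holds better for individual, less common events.

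Finally, SAP 9.7 and 6.1 disclose unequal follow-up. They let a reader approximate total time on drug, but not time at risk for a given event, so they do not close the gap.

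**Conclusion.** The concern holds for the visible text. The crude percentages are not wrong, but alone they cannot support a statement about risk over 26 weeks if dropout is near the planned level. Under constant, independent hazards they run about 19% below the 26-week risk for events of 5% to 20%. For a true 10%, the tested dropout timings give 7.4% to 9.7%. Early-onset events are almost unaffected; events starting after Week 12 lose about 28%. The effect on parent-group contrasts is small. The change is worth making because it concerns the primary safety summary and costs little; the plan is not invalid without it.

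**What to change.** In SAP 9.1, keep the crude percentages and add the following:

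- Beside each percentage, the number of subjects with a first event per 100 patient-years, with time counted from first open-label dose to the earlier of first event and last dose plus 21 days.
- For any TEAE, serious TEAEs and EPS-related TEAEs (the SAP's five categories), a Kaplan-Meier cumulative incidence at Week 26 with 95% CI, censored at the end of that same window and labelled as assuming non-informative censoring.
- For TEAEs leading to discontinuation, the crude proportion, or a cumulative incidence with other discontinuation as the competing event; not Kaplan-Meier.
- A sentence that any 26-week risk reported for the three Kaplan-Meier classes is taken from that column.

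The cost is SAP wording and a few table columns from dates already collected, with no protocol change. There are two drawbacks to state in the SAP. The rate is a fair summary only if the hazard is roughly constant. Kaplan-Meier's censoring assumption may fail, because subjects may leave through dissatisfaction, adverse events or need for disallowed treatment (Protocol 3.8.3.2).
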